8.1.3 Objective Response Rate (ORR)

Target : Analysis set

population

n

Endpoint : **Objective Response Rate (ORR)**

Statistical analysis : For the end point in the avelumab maintenance and first-line chemotherapy, the number of patients included, the number of responders, and the response rate will be calculated along with its 95% confidence interval. In addition, summary statistics will be calculated for the number of cycles at the time of determination of best overall response.

The denominator for each proportion (%) will be the analysis set, and patients with missing value for the end point will be excluded from the denominator.

Clopper-Pearson method will be used to calculate the confidence

interval.

[Division of categorical variables]

Factor	区分
Response	Objective response/ Non-objective response

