9. RESEARCH METHODS

9.1. Study design

This study is a multicenter, non-interventional, retrospective, medical chart review of locally advanced or metastatic UC patients who were prescribed avelumab as 1L maintenance therapy between 24 February 2021 and 30 November 2021 in Japan. All decisions regarding clinical management and treatment of the participating patients were made by the investigator as part of standard care in a real-world clinical setting and were not contingent upon the patient's participation in the study. Data will be collected if available per study site.

- Index date: The date of first prescription for avelumab between 24 February 2021 (launch date of avelumab) and 30 November 2021
- Observation period: Patients will be followed from index date to 30 Jun 2022

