9.2.3. Definition of endpoints

9.2.3.1. Time to treatment failure (TTF)

TTF is defined as the following:

TTF, defined as the time from start of avelumab maintenance therapy to the date of end of treatment due to any cause including death. If there is no record of the end of treatment, it be discontinued on the last observation date during the study period.

9.2.3.2. rwPFS

rwPFS is defined as the following:

The time from start of avelumab maintenance therapy to date of first disease progression (as

clinically assessed by local investigator based on radiology, laboratory evidence, pathology, or other assessments) or death due to any cause, whichever occurred first. If there were no clinical records of death or disease progression, they will be censored at the date of initiation of the next line of therapy for the patients undertaking 2 or more lines of therapy (subsequent therapy after avelumab maintenance therapy) based on the record, or at their last observation date during the study period for the patients undertaking only 1 line of therapy (only avelumab maintenance therapy) based on the record.

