5.1 Analysis set/populations

Among patients who were enrolled in the study and received maintenance avelumab treatment between 24 February 2021 and 30 November 2021, patients meeting all the inclusion criteria will be analyzed.

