5.2 Handling of missing values

An absence of data for analysis will be treated as missing values, and no special imputation processing will be performed using statistical methods.

However, if there are specifications for handling of missing values in subsequent each specification, they are followed.

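### Avelumab ORR is planned only among patients with a recorded response assessment, and no readable text plans a rate over the full analysis set beside it

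*SAP*

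**What the plan says.** SAP 8.1.3 covers ORR on avelumab and on first-line chemotherapy. It opens with a full denominator, "The denominator for each proportion (%) will be the analysis set", and in the same sentence removes unassessed patients: "patients with missing value for the end point will be excluded from the denominator". For output, "the number of patients included, the number of responders, and the response rate will be calculated" with a 95% Clopper-Pearson interval. The response factor has two levels, "Objective response/ Non-objective response". SAP 5.5 builds them from CR or PR against SD or PD.

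Four other places bear on this:

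- SAP 5.1 sets the population by eligibility alone: "patients meeting all the inclusion criteria will be analyzed". The criteria in Protocol 9.3.1 concern diagnosis, start of avelumab in the window, and consent. None requires a tumour assessment.
- SAP 5.2 says that "no special imputation processing will be performed using statistical methods", but lets individual sections set their own rule.
- Protocol 9.1 warns that "Data will be collected if available per study site".
- Protocol 9.2.3.2 counts progression "or death due to any cause, whichever occurred first" as the rwPFS event. Protocol 9.2.3.1 counts end of treatment for any cause, including death, as the TTF event.

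**The concern.** The efficacy endpoints do not rest on the same patients. Someone who dies a few weeks into avelumab with no scan on file counts against the drug in TTF and rwPFS. In ORR the same patient may have no category to fall into and so leaves both numerator and denominator. If unassessed patients are mostly early failures, the printed response rate is too high, and nothing printed beside it shows by how much.

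Missing responses are foreseeable in a chart review, and Protocol 9.10 acknowledges missing variables in general terms. The SAP gives other endpoints more care on this kind of question: TTF has a sensitivity analysis (8.1.1), and corticosteroid use and later treatment have Unknown and Missing categories (8.2.1, 8.2.4). ORR has neither. It is one of four efficacy endpoints serving the effectiveness objective, so the printed rate is likely to be quoted.

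**Working it through.** There is no planned figure to reproduce. The readable text gives no expected ORR, missing rate or precision target, and the expected number of patients in Protocol section 6 is blacked out. All numerical inputs below are assumptions.

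**Notation.** N = analysis set, m = patients with no recorded response, r = recorded responders, q = response rate the m patients would have shown if assessed.

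- Planned rate: r/(N − m)
- Full-set rate, missing counted as non-response: r/N
- Rate had everyone been assessed: (r + m·q)/N
- Error of the planned rate: (m/N)·[r/(N − m) − q]
- Error of the full-set rate: −(m/N)·q

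The planned rate therefore errs upward only when q is below r/(N − m). The full-set rate never errs upward. For q between 0 and r/(N − m), the two bracket the truth.

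**Ratio of the two rates.** This is N/(N − m), or 1/(1 − m/N), for any N: 1.05 at 5% missing, 1.11 at 10%, 1.25 at 20%, 1.43 at 30%.

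**Rates and exact intervals, assuming N = 100 and r = 20:**

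| Missing | Planned rate (95% CI) | Full-set rate (95% CI) |
|---|---|---|
| 5 | 20/95 = 21.1% (13.4–30.6) | 20/100 = 20.0% (12.7–29.2) |
| 10 | 20/90 = 22.2% (14.1–32.2) | same |
| 20 | 20/80 = 25.0% (16.0–35.9) | same |
| 30 | 20/70 = 28.6% (18.4–40.6) | same |

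**Error in percentage points, same N and r:**

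| m | q | Rate if all assessed | Planned | Full set |
|---|---|---|---|---|
| 10 | 0% | 20.0% | +2.2 | 0 |
| 10 | 10% | 21.0% | +1.2 | −1.0 |
| 10 | 22.2% | 22.2% | 0 | −2.2 |
| 10 | 40% | 24.0% | −1.8 | −4.0 |
| 20 | 0% | 20.0% | +5.0 | 0 |
| 20 | 10% | 22.0% | +3.0 | −2.0 |
| 20 | 25% | 25.0% | 0 | −5.0 |
| 20 | 40% | 28.0% | −3.0 | −8.0 |

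In the 40% rows both rates are too low, so the bracket fails when unassessed patients respond more often than assessed ones.

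**First-line ORR.** The same denominator rule applies, but the early-death mechanism does not: every included patient lived to start avelumab (Protocol 9.3.1, criterion 2).

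**Complete responses already present at entry.** Protocol 9.2.3.3 defines response as a best result of CR or PR, and Protocol 9.3.2 excludes nobody, so a patient in CR when avelumab starts could be counted as a responder. Assume N = 100, 10 new responders, nothing missing, and every entry CR counted. Five entry CRs then give 15/100 = 15.0%, against 10/95 = 10.5% in the other patients. Fifteen give 25/100 = 25.0%, against 10/85 = 11.8%. These results follow directly from the chosen inputs and say nothing about this cohort.

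**The case against.** The rule is explicit, and the SAP reports both the number included and the number of responders. Anyone who knows the size of the analysis set can compute r/N and its interval. That stands, and it is why the point is minor. The full-set figure is nevertheless not a planned output, and the reasons for missing responses cannot be recovered from what is printed.

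Counting missing as non-response is itself a crude imputation and departs from the default in SAP 5.2. This is true, and the resulting rate is biased low if some missing responses are merely unrecorded. It is therefore proposed as a second figure, not a replacement, and SAP 5.2 allows section-specific rules.

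Early deaths may not go missing at all. Response is by investigator judgement, and a site could record clinical deterioration as PD, which keeps the patient in the denominator. Nothing readable says how sites coded such patients, so the mechanism is possible but not shown.

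A reader might go further and infer that the planned ORR is inflated by complete responses carried over from chemotherapy, and that the plan never separates them. The documents do not support that. SAP text between 8.2.5 and section 11 is blacked out and may hold a breakdown by first-line response. SAP 5.5 derives a first-line grouping that no readable analysis uses, although it pools CR with PR. Protocol 9.2.3.3 also ties response to RECIST 1.1 as far as practice allows, so silence on a reference baseline does not show that none applied. Finally, best first-line response is only a proxy for disease status when avelumab starts.

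**Conclusion.** The point holds as a minor, cheap improvement. The planned avelumab ORR covers only patients with a recorded assessment, and no readable text sets a full-analysis-set rate beside it. Under the assumed 100 patients and 20 responders, the gap between the two rates is 2.2 points with 10 missing and 5.0 points with 20 missing. Each gap lies well inside the exact interval of 12.7–29.2% around the full-set rate.

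The documents do not show that the planned rate is biased upward. That depends on whether unassessed patients respond less often than assessed ones, which cannot be known from the plan. Neither rate is correct by construction. The case for printing both is that together they bound the answer under a plausible condition. ORR is secondary and descriptive in a study whose primary endpoint is baseline characteristics, so no main conclusion turns on it.

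**What to change.** In SAP 8.1.3, for avelumab, keep the planned evaluable-only rate and add the rate over the full analysis set, with missing or not-evaluable counted as non-response. Give each its Clopper-Pearson interval. Show the number missing, split by death before assessment where the recorded dates allow. First-line ORR can keep its planned denominator.

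Optionally, unless the blacked-out sections already contain it, tabulate avelumab ORR by best first-line response, using the four-level variable listed in SAP 7.1 (CR, PR, SD, PD). Label it as a proxy for disease status at avelumab start.

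The cost is a few lines of SAP text and one or two tables from data already collected, with nothing further asked of sites. Protocol 9.8 requires the SAP to be final before data lock, and Protocol section 6 plans the lock for 31 January 2023, after SAP version 1.1 of 21 December 2022. The downside is a less favourable second figure that is itself too low if some missing patients responded. The report should say so.

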8.1.4 Real-world progression-free survival from chemotherapy (rwPFS-c)

Target : Analysis set

population

n

Endpoint : Real-world progression-free survival from chemotherapy (rwPFS-c)

Statistical analysis : For the endpoint, the median and its 95% confidence interval will be calculated using the Kaplan–Meier method. In addition, the Kaplan–Meier curve will be plotted, and the rwPFS-c rate for every 2 months and its 95% confidence interval will be calculated. Greenwood's formula will be used to calculate the confidence interval for the rwPFS-c rate.

In order to evaluate the overall observation period of the study, the median observation period will be calculated by estimating the reverse KM curve in which censoring patients are regarded as patients with events and patients with events are regarded as censoring patients.

8.2 Safety endpoints

8.2.1 Corticosteroid therapy for immune-related adverse events (irAEs)

Target : Analysis set

population

n

Endpoint : Continuous variable

Corticosteroid starting dose¹⁾ (prednisolone equivalent)

Duration of treatment with corticosteroid (days)

Categorical variable

Presence/absence of corticosteroid administration to irAE

Presence or absence of prednisolone

Presence or absence of methylprednisolone

	
Presence or absence of betamethasone
 
Presence or absence of dexamethasone
 
Presence or absence of hydrocortisone
 
Presence or absence of others
 
Details of other drugs

	
Presence or absence of treatment with non-high-dose corticosteroid (prednisolone-equivalent starting dose is less than 40)
 
Presence or absence of treatment with high-dose corticosteroid (prednisolone-equivalent starting dose is 40 mg or higher)
 
Presence or absence of steroid pulse therapy (prednisolone-equivalent starting dose is 625 mg or higher)

	
1) As the Instruction on the EDC and the EDC operation manual describes the instruction to “enter starting dose (dose change after the start of tapering is unnecessary)”, it is likely that only the starting dose is collected. However, if there is any entry of dose change (dose increase) according to the instruction, the dose should be used to determine the starting dose of corticosteroid (the maximum value of the starting dose of each case (including administration change) is used as the starting dose of corticosteroid. When administrations of multiple drugs overlap with the duration of administration, the total dose is considered to be the value of the starting dose.

Statistical analysis	
: The following aggregation will be performed for endpoints:
 
Summary statistics will be calculated for continuous variables.
 
A frequency table (number of cases, proportion [%]) will be created for categorical variables.
 
A frequency table (number of cases, proportion (%)) will also be created for details regarding other drugs.

【Category Variable Classification】

Factor	Division
Presence/absence of corticosteroid administration to irAE	Absence/Presence/Unknown/Missing
Presence or absence of prednisolone	Absence/Presence
Presence or absence of methylprednisolone	Absence/Presence

Presence or absence of betamethasone	Absence/Presence
Presence or absence of dexamethasone	Absence/Presence
Presence or absence of hydrocortisone	Absence/Presence
Presence or absence of others	Absence/Presence
Presence or absence of treatment with non-high-dose corticosteroid	Presence
Presence or absence of treatment with high-dose corticosteroid	Presence
Presence or absence of steroid pulse therapy	Presence

8.2.2 Premedication for potential infusion-related reaction of avelumab

Target : Analysis set

population

n

Endpoint : Premedication for potential infusion-related reaction of avelumab

Detailed name of the drug

Detailed name of the other drug

Statistical analysis : A frequency table (number of cases, proportion (%)) will be created for the endpoints.

【Division of categorical variables】

Factor	Division
Presence or absence of premedication for potential infusion-related reaction of avelumab	Absence/Presence/Unknown
Detailed name of the drug	Acetaminophen/diphenhydramine hydrochloride/chlorpheniramine maleate/Other

8.2.3 Treatment for infusion-related reaction of avelumab

Target : Analysis set

population

n

Endpoint : Treatment for infusion-related reaction of avelumab
Detailed name of the drug

Statistical analysis : A frequency table (number of cases, proportion (%)) will be created for the endpoints.

【Division of categorical variables】

Factor	Division
Presence or absence of treatment for infusion-related reaction of avelumab	Absence/Presence/Unknown

8.2.4 Regimen after avelumab maintenance therapy

Target : Analysis set
population

n

Endpoint : Continuous variable
Duration of Treatment after avelumab maintenance therapy (Days)

Categorical variable

Presence/absence of UC treatment after avelumab maintenance therapy
Regimen after avelumab maintenance therapy

Statistical analysis : The following aggregation will be performed for the end point.
For continuous variables, summary statistics will be calculated for each treatment. A frequency table (number of subjects, proportion (%)) will be created for the presence or absence of UC treatment after avelumab maintenance therapy.
A frequency table (number and proportion (%)) will be created for the second-line, third-line and subsequent treatment regimens for the second-line and subsequent treatment after avelumab maintenance therapy.

In addition, a listing of patients will be prepared.

【Division of categorical variables】

Factor	Division
Presence or absence of treatment after avelumab maintenance therapy	Absence/Presence/Unknown/Missing

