5.5 Derived variable

The items and definitions of variables whose derivation is necessary at the time of statistical analysis are shown below.

Continuous variable

Item	Derivation method
Treatment-free interval: Time from the end date of first-line chemotherapy to the start date of avelumab administration (days)	Start date of initial administration with avelumab – end date of first-line chemotherapy administration + 1
Duration of treatment of first-line chemotherapy (days)	End date of first-line chemotherapy administration – start date of first-line chemotherapy administration + 1
Duration of treatment (irAE treatment) of corticosteroid (days)	End date of corticosteroid administration – start date of corticosteroid administration + 1
Time to treatment failure of avelumab (TTF)	Defined as the period from the date of start of avelumab to the date of end of treatment* for any reasons including death. If there is no record of end of treatment, patients will be censored at the date of last observation during the study period. *The following sensitivity analysis will also be performed. Considering its clinical meaning, "interruption due to being well-controlled" does not correspond to "treatment failure"; it should be treated as an event on the day when the death or discontinuation was observed prior to the last observation date. If no death or discontinuation occurred before the date of the last observation, data will be censored at the date of the last observation.
Real-world progression-free survival (rwPFS)	Defined as the period from the start date of avelumab maintenance therapy to the date of first

	
disease progression (clinical evaluation based on imaging examinations, laboratory tests, and pathological tests, as well as other evaluations by the investigators of each institution) or death from any cause, whichever occurs earlier.
 
If there is no record of death or disease progression, patients on second or later lines (following avelumab maintenance therapy) will be censored at the start of the second-line treatment, and patients on only avelumab maintenance therapy will be censored at the date of the last visit during the study, based on the medical record.

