Real-world progression-free survival from chemotherapy (rwPFS-c)	
Defined as the period from the start date of first-line chemotherapy to the date of first disease progression (clinical evaluation based on imaging examinations, laboratory tests, and pathological test, as well as other evaluations by the investigators of each institution) or death from any cause, whichever occurs earlier.
 
If there is no record of death or disease progression, patients on second or later lines (following avelumab maintenance therapy) will be censored at the start of the second-line treatment, and patients on only avelumab maintenance therapy will be censored at the date of the last visit during the study, based on the medical record.

Starting dose of corticosteroid (Steroid equivalent dose)	Calculate according to “5.4 Steroid equivalent dose (prednisolone-equivalent dose.”
Duration of treatment of corticosteroid (days)	Last administration date – date of first administration of the first steroid drug + 1
Duration of treatment of avelumab maintenance (days)	Last administration date – date of first administration + 1.
Duration of treatment of each regimen (days)	Last administration date – date of first administration + 1.

Categorical variable

Item	Derivation method
Age (2 divisions)	Age is divided into the following categories: <65 years/65 years or older
Site of primary tumor (2 divisions)	The primary site is divided into the following categories: "upper urinary tract" for renal pelvis or ureter "lower urinary tract" for bladder and urethra
Tumor histological type (2)	The histological types are divided into the following categories. "Urothelial carcinoma" for urothelial carcinoma "Non-urothelial carcinoma" for adenocarcinoma, squamous cell carcinoma, small cell carcinoma, or others
Presence or absence of visceral metastasis	"Presence" will be selected if the metastatic site is "lung," "liver," "adrenal gland," "pancreas," "kidney," "spleen," or "other" which is regarded as visceral metastasis. If the metastatic site is not regarded as visceral metastasis, "absence" will be selected.
Presence or absence of non-visceral metastasis	"Presence" will be selected if the metastatic site is "bone," "distant lymph nodes," or "other" which is regarded as non-visceral metastasis. If the metastatic site is not regarded as non-visceral metastasis, "absence" will be selected.

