6.3 Details of statistical analysis

6.3.1 Summary statistics

If summary statistics is described in this plan, the following values will be calculated unless otherwise specified.

Number of subjects, number of subjects with missing, mean, standard deviation, minimum value, quartile point (25% point, 50% point [median], 75% point), maximum value

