8.1 Efficacy endpoints

8.1.1 Time to treatment failure (TTF) of avelumab

Target : Analysis set

population

n

Endpoint : Time to treatment failure (TTF) of avelumab

Statistical analysis : For the endpoint, the median and its 95% confidence interval will be calculated using the Kaplan–Meier method. In addition, the Kaplan–

Meier curve will be plotted, and the TTF rate for every 2 months and its 95% confidence interval will be calculated. Greenwood's formula will be used to calculate the confidence interval for the TTF rate.

In order to evaluate the overall observation period of the study, the median observation period will be calculated by estimating the reverse KM curve in which censoring patients are regarded as patients with events and patients with events are regarded as censoring patients.

In addition, as a sensitivity analysis, " interruption due to being well-controlled" will be treated as an event based on the day when death or discontinuation was observed before the date of the last

observation, and if no death or discontinuation or death occurred before the date of the last observation, data will be censored at the date of the last observation.

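### Duration of each post-avelumab regimen has no rule for regimens still running at the 30 June 2022 cutoff, so its summary is too short to the extent regimens are ongoing

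*SAP*

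**What the plan says.** SAP 8.2.4 names the number of days on treatment after avelumab maintenance as its continuous endpoint and adds "For continuous variables, summary statistics will be calculated for each treatment". SAP 6.3.1 fixes what those statistics are: "Number of subjects, number of subjects with missing, mean, standard deviation, minimum value", then the quartiles and the maximum. SAP 5.5 gives the formula for each regimen as "Last administration date – date of first administration + 1", with no status flag and no censoring rule.

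The only general rule that could reach an ongoing regimen is SAP 5.2: "An absence of data for analysis will be treated as missing values, and no special imputation processing will be performed using statistical methods". It does not mention ongoing treatment. Protocol 9.2.2 lists the drug name, start date and end date for these regimens and no item for ongoing status. Protocol 6 and 9.1 end observation on 30 June 2022.

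For time on avelumab, SAP 5.5 does deal with the open-ended case in its TTF definition: "If there is no record of end of treatment, patients will be censored at the date of last observation during the study period". SAP 8.1.1 then analyses TTF accordingly: "For the endpoint, the median and its 95% confidence interval will be calculated using the Kaplan–Meier method".

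**The concern.** A later regimen starts only after avelumab stops, inside the same fixed observation window, so it has less time to finish than avelumab had. Some will still be running on 30 June 2022. Their full length is unknown, yet the stated analysis treats every duration either as known or as absent.

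At stake is one descriptive table. Without a label, its median would be read as time on second-line or later treatment when part of it is only time to the cutoff. Secondary objective 4, to describe patterns of subsequent therapy, is answered mainly by the regimen frequency tables, which do not depend on duration.

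**Working it through.** The plan states no figure for this endpoint, so there is none to reproduce. The check has three parts.

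**1. Follow-up, from the documents.** First avelumab prescription falls between 24 February and 30 November 2021; observation ends 30 June 2022.
- Shortest: 30 Nov 2021 to 30 Jun 2022 = 212 days; 212/30 = 7.1 months (30-day months, SAP 5.3).
- Longest: 24 Feb 2021 to 30 Jun 2022 = 491 days; 491/30 = 16.4 months.

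Avelumab, any gap and all later regimens share this window.

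**2. Direction.** Let T be the true regimen duration and C the time from regimen start to cutoff. The regimen is ongoing if T > C.
- Cut at the last recorded dose (the reading closest to SAP 5.5): the analysed value is about min(T, C), which never exceeds T.
- Dropped for a blank end date (SAP 5.2): the analysed values are those T with T ≤ C. With C independent of T, the mean of T given T ≤ C is at most the mean of T.
- Censored, as for TTF: Kaplan–Meier on min(T, C), with the event being T ≤ C, recovers the median under the same independence.

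Both uncensored readings are short.

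**3. Size, by simulation; every input below is assumed.** Follow-up uniform on 7.07–16.37 months; avelumab TTF exponential with median 3, 6 or 9 months; gap 0 or 1 month; regimen duration exponential with median 2, 4 or 6 months; only patients who start the next regimen before cutoff are kept. This gives 3 × 2 × 3 = 18 cases, 1,000,000 patients each.

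| Case (TTF median, gap, regimen median; months) | Ongoing | Median if cut | Median if dropped |
|---|---|---|---|
| Mildest (3, 0, 2) | 12% | 7% short | 14% short |
| Middle (6, 0, 4) | 34% | 3.03 months | 2.47 months |
| Most severe (9, 1, 6) | 52% | 42% short | 56% short |

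In the middle case the shortfall is (4.0 − 3.03)/4.0 = 24% if cut and (4.0 − 2.47)/4.0 = 38% if dropped. The Kaplan–Meier median is within 0.2% of the true value in all 18 cases.

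**Sensitivity.**
- Short regimens (median 0.5–1.5 months, no gap, under 10% ongoing): 2–9% ongoing; 2–8% short if cut, 2–10% if dropped.
- Correlation of −0.3 to 0.5 between avelumab time and regimen duration: cut median 5–45% short; Kaplan–Meier off by −6% to +7%.
- Earlier or later entry, and Weibull shape 1 or 1.5: 5–58% ongoing; cut median 3–47% short; Kaplan–Meier within 0.2%.

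**Small groups** (10,000 replicates; Kaplan–Meier medians not reached are left out of its RMSE; RMSE in months).

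| Case | n | RMSE, Kaplan–Meier | RMSE, cut |
|---|---|---|---|
| Middle | 15 | 1.72 | 1.35 |
| Middle | 30 | 1.21 | 1.17 |
| Middle | 60 | 0.82 | 1.07 |
| 52% ongoing | 15 | 2.18 | 2.67 |

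In the middle case at n = 15 the bias is +0.3 months for Kaplan–Meier and −0.9 for the cut median. With 52% ongoing and n = 15, the Kaplan–Meier median is not reached in 14% of replicates.

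**The case against.** The strongest reply is that this is a consistent convention. SAP 5.5 derives the duration of avelumab maintenance with the same formula and no censoring, and the chemotherapy and corticosteroid durations are also plain date differences. On that view, date differences measure observed exposure, Kaplan–Meier is reserved for time-to-event endpoints, and only a label is missing. This stands in part: as observed exposure the figure is correct, but the SAP does not call it that. Time on avelumab also gets a censored analysis through TTF; later regimens get none.

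Sites could have entered end dates after 30 June 2022, since data collection ran to 30 November 2022. The SAP makes no provision for this, and it would only shrink the shortfall.

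The number missing (SAP 6.3.1) and the patient listing (SAP 8.2.4) may reveal dropped regimens. The number missing would not count regimens cut at the cutoff, the listing's contents are not specified, and neither corrects the summary. Redacted SAP text cannot be checked.

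The statistics are per treatment, so groups may be small, and there Kaplan–Meier can be the less accurate estimate. This stands. In the mildest case its RMSE is still higher at n = 60 (0.39 against 0.35 months). It limits where the Kaplan–Meier median is useful, but not the need for the ongoing count and the label.

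It is also true that the simulation covers only the first post-avelumab regimen, while 8.2.4 tabulates third and later lines too.

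**Conclusion.** The concern holds, as a minor point. Followed as written, SAP 5.5 and 8.2.4 give regimen durations that are too short to the extent regimens are ongoing at cutoff, on either reading. The direction follows from the rules, given independence for the dropped reading; the size does not, because it depends on an ongoing share the documents do not give. Under the 18 assumed cases the median is 7–42% short if ongoing regimens are cut and 14–56% short if they are dropped; if few are ongoing, the loss is slight. The primary endpoint, TTF and rwPFS do not change.

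**What to change.** Amend SAP 8.2.4 so that, for each regimen:

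1. the number still ongoing at cutoff is reported;
2. the existing summary statistics are kept but labelled *observed duration to 30 June 2022*;
3. a Kaplan–Meier median with 95% CI is added, counting an ended regimen as the event and censoring an ongoing one at last observation, no later than the cutoff.

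Where the group is small or the Kaplan–Meier median is not reached, items 1 and 2 suffice. The SAP should set the group size below which item 3 is omitted.

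The cost is SAP wording and reuse of the TTF program. The documents do not show whether the EDC records ongoing status, so some site queries may be needed to tell an ongoing regimen from an unrecorded end date.
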